#### **9.5 Rescue treatment**

If medically necessary (i.e., to control intolerable AD symptoms), rescue treatment for AD may be provided to trial subjects at the discretion of the investigator.

If possible, investigators should attempt to limit the first step of rescue therapy to topical medications, and escalate to systemic medications only for subjects who do not respond adequately after at least 14 days of topical treatment.

Subjects who receive topical rescue treatment (TCS of any WHO class [see [Appendix 8](#)], or TCI) will continue treatment with IMP (tralokinumab/placebo) and will receive the vaccines. TCI may be used for rescue, but should be reserved for body areas where TCS is not advisable or on areas where continued treatment with TCS is considered unsafe.

If a subject receives rescue treatment with systemic corticosteroids or non-steroidal systemic immunosuppressive drugs (cyclosporine, methotrexate, mycophenolate mofetil, azathioprine, etc.), IMP will be immediately discontinued (see Section [10.2.2](#), reasons for temporary discontinuation of IMP). After the treatment with these medications is completed, IMP may

be resumed if deemed appropriate by the investigator and sponsor's medical expert, but not sooner than 5 half-lives after the last dose of systemic rescue medication.

Investigators should make every attempt to conduct efficacy and safety assessments (for example disease severity scores [IGA and EASI], safety labs) immediately before administering any rescue treatment. An unscheduled visit may be used for this purpose, if necessary.

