**Panel 6: Prohibited medication**

Medication	Prohibited from	Prohibited to	Temporary discontinuation of IMP required
Topical medications used for treatment of AD, including: 
 
• TCS of any WHO class.
 
• TCI.
 
• PDE-4 inhibitors.
 
	Week -2 (2 weeks prior to randomisation)	Week 16 (end of treatment)	No
Use of UVA or UVB, psoralen + UVA (PUVA), other phototherapy, or tanning beds.	Week -6 (6 weeks prior to randomisation)	Week 16 (end of treatment)	No
Three or more bleach baths per week.	Week -4 (4 weeks prior to randomisation)	Week 16 (end of treatment)	No
Investigational agents other than tralokinumab.	3 months or 5 half-lives  prior to randomisation	Week 30 (safety follow-up)	Yes
Immunoglobulin.	3 months or 5 half-lives  prior to randomisation	Week 30 (safety follow-up)	Yes
Blood products.	4 weeks prior to screening	Week 30 (safety follow-up)	Yes
Systemic corticosteroids 	Week -4 (4 weeks prior to randomisation)	Week 30 (safety follow-up)	Yes
Systemic treatment for AD with an immunosuppressive or immunomodulating agent  .	Week -4 (4 weeks prior to randomisation)	Week 30 (safety follow-up)	Yes
Allergen immunotherapy.	Randomisation	Week 30 (safety follow-up)	Yes
Vaccination of any kind (except influenza virus vaccines).	3 months prior to screening	Week 30 (safety follow-up)	Yes

1) Whichever is longer. For cell-depleting agents, the use is disallowed within 6 months of randomisation.

2) Note: nasal and inhaled corticosteroids are allowed.

3) Examples include cyclosporine, mycophenolate mofetil, azathioprine, methotrexate, Janus kinase inhibitors, interferon-gamma, dupilumab, and other biologics.

AD, atopic dermatitis; IMP, investigational medicinal product; PDE-4, phosphodiesterase 4; TCI, topical calcineurin inhibitor; TCS, topical corticosteroid; UV, ultraviolet; WHO, World Health Organization.

In case any prohibited treatments are used during the trial, they must be recorded as concomitant medication.

Refer to Section 9.5 for principles for use of rescue treatment and re-initiation of IMP after discontinuation of prohibited systemic rescue treatment.

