### 14.3.6.2 Primary estimand: ‘composite’

The primary estimand for the first 2 secondary endpoints will be:

- Treatment difference in response rates of IGA 0/1 and EASI75 after 16 weeks achieved without rescue medication, regardless of treatment discontinuation.

The primary estimand assesses the expected difference in response rates (defined as response obtained without initiation of any rescue medication) after 16 weeks, resulting from initiation of a treatment regimen with tralokinumab compared to a treatment regimen with placebo.

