#### Primary analysis for the primary estimand

Data retrieved at Week 16 for subjects who have permanently discontinued IMP prior to Week 16 will be included in the analysis. Subjects who prior to the Week 16 visit have received rescue medication will be considered non-responders, reflecting an assumption that initiation of rescue medication indicates failure of the randomised treatment to achieve response, and that a (possible) observed positive response after initiation of rescue medication is not attributable to the randomised treatment. Missing data for subjects who did not attend the Week 16 visit and where rescue medication has not been used prior to Week 16, will be imputed as non-responders.

The difference in response rates between treatment groups will be analysed using the Cochran-Mantel-Haenszel test stratified by baseline disease severity (IGA 3 or 4). The treatment estimate and the corresponding 95% CI will be presented. The null hypothesis of no difference in response rates between tralokinumab and placebo will be tested against the 2-sided alternative that there is a difference.

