The criteria related to systemic rescue medication in the definition of the per protocol analysis set have been updated relative to the protocol text to include, not only those for the AD indication but all systemic immunosuppressive treatments irrespectively of indication. The referred criteria for excluding patients consequently become:

- Initiated systemic immunosuppressive treatment prior to Week 10 and who are still treated with or exposed to the given treatment at Week 10 (that is, Week 10 [visit 8] occurs within 5 half-lives after the last dose of the given systemic immunosuppressive medication).
- Initiated systemic immunosuppressive treatment at any time point from Week 10 to Week 16.

The rationale for excluding these subjects is to ensure that subjects were not immunosuppressed by these treatments when the vaccinations were administered, as this might impact the response to the vaccination, and thereby the primary endpoints. This is independent of the indication for the immunosuppressive treatments and should therefore include all subjects treated with systemic immunosuppressants, irrespectively of the indication.

In addition to the criteria specified in the protocol, subjects with Week 16 visit occurring ≥ 56 days after the Week 12 visit, are not included in per protocol analysis set due to a too long interval between administration of the vaccine and measurement of the vaccine response, since this would induce a risk of a perished vaccine response.

Systemic immunosuppressive treatment definition

ATC2 code H02 or L04 will be used to identify administered systemic immunosuppressive treatments. [Table 1](#) below presents the medications that as minimum will be identified in the trial (as being systemic immunosuppressive) along with the half-lives applied to evaluate the PP exclusion criteria.

Medications administered in the screening period will be included in the search to ensure that all administered medications that could potentially be immunosuppressive at time of vaccination will be covered. Different routes of administration can be used for the medications, which will result in different half-lives.

Table 1: Systemic immunosuppressive treatments and applied halflives

ATC 4	ATC 4 TERM	Standardized Medication Name	Route of Administration	Halflife		
				Hours	Weeks	5 x t _{1/2} ¹
H02AB	GLUCOCORTICOIDS	DEXAMETHASONE	ORAL	7.2	0.0	0.2

H02AB	GLUCOCORTICOIDS	DEXAMETHASONE SODIUM PHOSPHATE	INTRAVENOUS	24	0.1	0.7

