6.3 Rescue medication

Rescue medication is defined by the following algorithm: Concomitant medications with Dermatitis atopic or Dermatitis infected as the preferred term for the indication and either ATC2 code H02 or D07, or ATC4 code D11AH, or preferred name Methotrexate, Ciclosporin, Azathioprine, Mycophenolate-mofetil, Mycophenolate-sodium, Mycophenolate-acid, or Dupilumab.

According to the protocol, investigators should make every attempt to conduct efficacy and safety assessments immediately before administering any rescue treatment. Therefore, if rescue medication has start date the same day as an efficacy assessment, then the assumption will be that the assessment is not influenced by the rescue medication.

The table of rescue medication will include medications taken after the first dose and before the Week 16 visit (or before day $7 \times 16 = 112$ after first dose, in case the Week 16 visit did not take place).

Rescue medication will be summarised for the treatment period. In addition, a summary table of rescue medication by type (topical and systemic) and by overall group (corticosteroids, immunosuppressants, and other) will be made.

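### The SAP's rescue-medication rule omits ATC2 L04, so an unlisted immunosuppressant given for AD would leave a Week 16 responder counted as a responder

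*SAP*

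**What the plan says.** Protocol 9.5 describes systemic rescue as systemic corticosteroids or "non-steroidal systemic immunosuppressive drugs (cyclosporine, methotrexate, mycophenolate mofetil, azathioprine, etc". The list of examples is left open. After such treatment IMP may resume, "but not sooner than 5 half-lives after the last dose of systemic rescue medication".

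Under the composite estimand (Protocol 14.3.6.2), a response is "defined as response obtained without initiation of any rescue medication". The primary analysis applies this directly: "Subjects who prior to the Week 16 visit have received rescue medication will be considered non-responders". Otherwise Week 16 data are used as observed, even after permanent discontinuation of IMP.

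SAP 6.3 turns rescue medication into a coding rule. The indication must be coded to atopic or infected dermatitis. The drug must also carry ATC2 H02 or D07, or ATC4 D11AH, "or preferred name Methotrexate, Ciclosporin, Azathioprine, Mycophenolate-mofetil, Mycophenolate-sodium, Mycophenolate-acid, or Dupilumab". There is no catch-all and no medical review step.

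SAP 5, which revises the per protocol set, uses a different search: "ATC2 code H02 or L04 will be used to identify administered systemic immunosuppressive treatments". Its Table 1 gives a minimum list of the drugs this search will find.

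**The concern.** The two SAP sections share H02, but where SAP 5 has the class L04, SAP 6.3 has seven drug names. Any L04 drug outside those names is invisible to the rescue rule, even when prescribed for AD.

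Rescue status determines who is a non-responder for IGA 0/1 and EASI75, the two confirmatory secondary endpoints. It does the same for EASI50, EASI90, SCORAD50 and SCORAD75. It also decides which data are dropped from the hypothetical-estimand and repeated-measurements analyses (Protocol 14.3.6.3 and 14.3.7), and which subjects have their worst EASI value carried forward in the SAP's added composite analysis (SAP 6.7). A missed rescue drug would leave a response on rescue credited to the randomised arm.

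**Working it through.** **1. Which drugs fall through.** SAP Table 1 lists six L04 agents. Compared with the rule in SAP 6.3:

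| Table 1 agent | ATC4 | Caught by SAP 6.3? |
|---|---|---|
| Dupilumab | L04AC | Yes, by name |
| Azathioprine | L04AX | Yes, by name |
| Methotrexate | L04AX | Yes, by name |
| Mycophenolate sodium | L04AA | Yes, by name |
| Nemolizumab | L04AC | No |
| Baricitinib | L04AA | No |

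Table 1 is a minimum list, so other L04 drugs could be missed too.

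**2. Who is affected.** The subject must take an unlisted L04 drug for AD before Week 16, attend Week 16, and meet IGA 0/1 or EASI75. "Missing data for subjects who did not attend the Week 16 visit and where rescue medication has not been used prior to Week 16" are already imputed as non-response, so non-attenders are not at issue.

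**3. Which other analyses catch the case.** Half-lives are from Table 1. The Week 14 dose is at Day 98 (Day 101 with the 3-day window) and Week 10 is Day 70.

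- *Nemolizumab:* 5 × 432 h = 2160 h = 90 days. IMP can resume by Week 14 only if the last dose falls by Day 98 − 90 = 8 (101 − 90 = 11 with the window). A later start with IMP doses still due should be recorded as permanent discontinuation. Sensitivity analysis 1 then makes the subject a non-responder, and the hypothetical and repeated-measurements analyses drop the later data. Because 90 days exceeds the 70 days to Week 10, and starts from Week 10 on are excluded anyway, the per protocol repeat removes every on-treatment case.
- *Baricitinib:* 5 × 12.5 h = 62.5 h = 2.6 days. A course over by Day 98 − 2.6 = 95.4 lets IMP resume by Week 14. Sensitivity analysis 1 and the data exclusions then miss it. The per protocol repeat keeps the subject only if the course ended by Day 70 − 2.6 = 67.4, the Week 8 and Week 10 doses were given, and no more than 2 doses were missed. A course of up to 14 − 2.6 = 11.4 days between doses need cost no dose.

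The residual gap is mainly a short course of a short-half-life drug with IMP resumed. None of these analyses changes the primary FAS result.

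**4. Effect on the result.** The planning inputs (Protocol 14.1) reproduce the plan's joint power of about 89%. Each non-inferiority test has power Φ(0.25/√(2 × 0.8 × 0.2/80) − 1.96) = 0.977. IGA 0/1 (30% v 10%) has 0.948 and EASI75 (40% v 15%) has 0.981, at 100 per arm. The product is 0.977² × 0.948 × 0.981 = 0.888.

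I took those planning rates as the observed counts and moved misclassified tralokinumab responders to non-response. The method is the CMH test without continuity correction, and the Mantel-Haenszel risk difference with Greenland-Robins variance. I assumed a 50:50 split between IGA 3 and 4, with equal response in both strata.

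| Endpoint | Responders (tralokinumab v placebo) | Difference, points (95% CI) | p |
|---|---|---|---|
| IGA 0/1 | 30 v 10 | 20 (9.3 to 30.7) | 0.0004 |
| | 29 v 10 | 19 (8.3 to 29.7) | 0.0007 |
| | 27 v 10 | 17 (6.5 to 27.5) | 0.002 |
| | 20 v 10 | 10 | 0.049 |
| | 19 v 10 | 9 | 0.072 |
| EASI75 | 40 v 15 | 25 (13.1 to 36.9) | 0.0001 |
| | 39 v 15 | 24 (12.2 to 35.8) | 0.0001 |
| | 37 v 15 | 22 (10.2 to 33.8) | 0.0004 |
| | 27 v 15 | 12 | 0.038 |
| | 26 v 15 | 11 | 0.055 |

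Significance is lost at 30 − 19 = 11 reclassified for IGA 0/1 and 40 − 26 = 14 for EASI75. If the misclassified subject is on placebo, the correction runs the other way: 30 v 9 gives 21 points (p = 0.0002), and 40 v 14 gives 26 points (p = 0.00004).

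**The case against.** The two searches serve different purposes. SAP 5 removes subjects who might be immunosuppressed at vaccination, whatever the indication. SAP 6.3 defines AD rescue for efficacy. One may be wider than the other without contradiction, and closing an open-ended list before unblinding is ordinary prespecification. Protocol 9.5 does not say that its open list means every L04 agent. Panel 6 note 3 ("Examples include cyclosporine, mycophenolate mofetil, azathioprine, methotrexate, Janus kinase inhibitors, interferon-gamma, dupilumab, and other biologics") sits under a wider heading that includes immunomodulating agents, and concerns prohibited drugs rather than rescue. Table 1 covers all indications, the screening period and wash-out drugs, so it does not show that anyone took nemolizumab or baricitinib for AD on treatment. The half-life limits assume that these drugs count as systemic rescue.

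The limits on Table 1 and Panel 6 stand. The argument that SAP 6.3 merely closes the list does not, for two reasons. First, SAP 5 describes its change as extending the systemic rescue criteria from the AD indication to any indication. It thereby treats systemic rescue as the AD part of systemic immunosuppressive treatment, which it finds by H02 or L04. Second, SAP 6.3 itself adds dupilumab, which Protocol 9.5 does not name. Table 1 puts nemolizumab in the same ATC4 class, and no reason is given for treating the two differently. On that reading the half-life limits are fair, since Panel 6 and Protocol 10.2.2 both send re-initiation after systemic rescue back to 9.5.

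**Conclusion.** The concern holds and is minor. The SAP 6.3 rule is narrower than the systemic rescue described in Protocol 9.5 and read in SAP 5, and nothing else in the plan corrects the primary FAS analysis of IGA 0/1 and EASI75. The documents give no count of affected subjects. Each one shifts the difference by about 1 point, for or against tralokinumab according to arm, and conclusions at the planning rates are unlikely to change. This rests on the Table 1 ATC codes and half-lives, the planned 100 per arm and the assumed stratum split. The vaccine-response primary endpoints do not use the SAP 6.3 definition.

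**What to change.** Before unblinding, add ATC2 code L04 to SAP 6.3 as a further alternative criterion, under the same two indication terms. Keep every current ATC code and all seven drug names, so that nothing now captured is lost. The cost is one clause and a rerun on blinded data of a search that SAP 5 already requires. If no subject qualifies, no result changes.

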6.4 Compliance

Compliance will be summarised and listed.

6.5 Exposure

The exposure time will be defined as detailed in Section 6.9.2. Exposure time will be summarised and listed.

Patient years of exposure (PYE) will be calculated as the difference between the start date and time and the end date and time divided by $60 \times 60 \times 24 \times 365.25$.

6.6 Vaccine responders

As stated in the protocol, a positive anti-tetanus response is defined as a 3-fold IgG increase at Week 16 compared to Week 12 if $\text{IgG} \leq 1.0 \text{ IU/mL}$ at Week 12; or $\text{IgG} \geq 2.5 \text{ IU/mL}$ if $\text{IgG} > 1.0 \text{ IU/mL}$ at Week 12.

As stated in the protocol, a positive anti-meningococcal response is defined as at least a 3-fold increase in specific IgG at Week 16 compared to Week 12.

The anti-meningococcal response is measured in separate assays against four individual meningococcal serogroup antigens, including serogroup A, C, W-135 and Y. To assess the vaccine response against a serogroup antigen a measurable specific IgG titer against that antigen at both week 12 and week 16 should be available. Subjects with a visit interval between Week 12 and Week 16 of ≥ 56 days are excluded from the analysis due to a too long interval between administration of the vaccine and measurement of the vaccine response.

In order to reduce the impact of missing data on the calculation of responders to the meningococcal vaccination the following will be applied:

- If data are available for 4 out of the four antigens, then the subject should be a responder against at least 3 of the antigens
- If data are only available for 3 out of the four antigens, then the subject should be a responder against these 3 antigens
- If data are only available for 2 out of the four antigens, then the subject should be a responder against these 2 antigens
- If data are only available for 1 out of the four antigens, then the subject should be a responder against this 1 antigen

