Main objectives and endpoints	
  
 Objectives	Endpoints	
   
 Primary objective	Primary endpoints	
 
 To demonstrate non-inferiority of tralokinumab versus placebo with respect to immune responses to concomitantly administered vaccines.	 
 
Positive anti-tetanus response at Week 16 (3-fold IgG increase compared to Week 12 if IgG ≤1.0 IU/mL at Week 12; or IgG ≥2.5 IU/mL if IgG >1.0 IU/mL at Week 12)
 
Positive anti-meningococcal response at Week 16 (IgG ≥3.0 mcg/mL with at least a 3-fold increase compared to Week 12)
 
 	
 
 Secondary objective	Secondary endpoints	
 
 To evaluate efficacy of tralokinumab concomitantly administered with vaccines.	 
 
Investigator Global Assessment (IGA) score of 0 (clear) or 1 (almost clear) at Week 16
 
At least 75% reduction in Eczema Area and Severity Index (EASI75) at Week 16
 
 	
 
 Additional secondary objective	Additional secondary endpoints	
 
 To evaluate safety and tolerability of tralokinumab concomitantly administered with vaccines.	 
 
Number of adverse events (AEs)
 
Presence of anti-drug antibodies
 
 	
  
	Objectives	Endpoints	Primary objective	Primary endpoints	To demonstrate non-inferiority of tralokinumab versus placebo with respect to immune responses to concomitantly administered vaccines.	
 
Positive anti-tetanus response at Week 16 (3-fold IgG increase compared to Week 12 if IgG ≤1.0 IU/mL at Week 12; or IgG ≥2.5 IU/mL if IgG >1.0 IU/mL at Week 12)
 
Positive anti-meningococcal response at Week 16 (IgG ≥3.0 mcg/mL with at least a 3-fold increase compared to Week 12)
 
	Secondary objective	Secondary endpoints	To evaluate efficacy of tralokinumab concomitantly administered with vaccines.	
 
Investigator Global Assessment (IGA) score of 0 (clear) or 1 (almost clear) at Week 16
 
At least 75% reduction in Eczema Area and Severity Index (EASI75) at Week 16
 
	Additional secondary objective	Additional secondary endpoints	To evaluate safety and tolerability of tralokinumab concomitantly administered with vaccines.	
 
Number of adverse events (AEs)
 
Presence of anti-drug antibodies
 

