## 6 Trial objectives and endpoints

### Panel 3: Objectives and endpoints

Objectives	Endpoints
Primary objective	Primary endpoints
To demonstrate non-inferiority of tralokinumab versus placebo with respect to immune responses to concomitantly administered vaccines.	
 
Positive anti-tetanus response at Week 16 (3-fold IgG increase compared to Week 12 if IgG <math>\leq</math>1.0 IU/mL at Week 12; or IgG <math>\geq</math>2.5 IU/mL if IgG >1.0 IU/mL at Week 12)
 
Positive anti-meningococcal response at Week 16 (IgG <math>\geq</math>3.0 mcg/mL with at least a 3-fold increase compared to Week 12)
 

Secondary objective	Secondary endpoints
To evaluate efficacy of tralokinumab concomitantly administered with vaccines.	
 
IGA score of 0 (clear) or 1 (almost clear) at Week 16
 
EASI75 at Week 16
 

Additional secondary objective	Additional secondary endpoints
To evaluate safety and tolerability of tralokinumab concomitantly administered with vaccines.	
 
Number of AEs
 
Presence of anti-drug antibodies
 

Other objectives	Other endpoints
To evaluate the efficacy of tralokinumab concomitantly administered with vaccines on severity and extent of AD and health-related quality of life.	
 
EASI50 at Week 16
 
EASI90 at Week 16
 
Change from baseline to Week 16 in EASI score
 
SCORAD75 at Week 16
 
SCORAD50 at Week 16
 
Change from baseline to Week 16 in SCORAD
 
Change from baseline to Week 16 in DLQI score
 
Change from baseline to Week 16 in EQ-5D-5L
 
Change from baseline to Week 16 in POEM
 
Change from baseline to Week 16 in HADS
 

AE, adverse event; DLQI, Dermatology Life Quality Index; EASI, Eczema Area and Severity Index; EASI50, at least 50% reduction in EASI score; EASI75, at least 75% reduction in EASI score; EASI90, at least 90% reduction in EASI score; EQ-5D-5L, EuroQoL 5-Dimension Health Questionnaire 5 Level; HADS, Hospital Anxiety and Depression Scale; IGA, Investigator's Global Assessment; POEM, Patient-Oriented Eczema Measure; SAE, serious adverse event; SCORAD, Scoring Atopic Dermatitis; SCORAD50, at least 50% reduction in SCORAD score; SCORAD75, at least 75% reduction in SCORAD score.

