## 12 Scientific rationale for trial design and appropriateness of assessments

This trial will assess immunisation responses against 2 different vaccines (a combined diphtheria, tetanus, and acellular pertussis vaccine and a meningococcal vaccine) in adults with moderate-to-severe AD who are treated with tralokinumab, to ensure a broad assessment of immune competence in subjects treated with tralokinumab.

Since concomitant administration of vaccines may affect the efficacy of tralokinumab in patients with AD, a placebo-controlled parallel group design has been chosen to evaluate the efficacy and safety of Q2W tralokinumab concomitantly administered with vaccines in the target patient population.

The vaccines will be given after 12 weeks of tralokinumab/placebo treatment to ensure that the trial drug effect has reached near-steady state levels when the vaccines are administered.

The vaccine responses will be analysed at Week 16 when the tralokinumab/placebo treatment schedule is complete. This allows an evaluation of the vaccine responses 4 weeks after vaccination which is the time span used to evaluate efficacy of these vaccine products (33, 34).

The trial will evaluate the percentage of subjects achieving a positive anti-tetanus response at Week 16 (defined as a 3-fold IgG increase compared to Week 12 if  $\text{IgG} \leq 1.0 \text{ IU/mL}$  at Week 12; or  $\text{IgG} \geq 2.5 \text{ IU/mL}$  if  $\text{IgG} > 1.0 \text{ IU/mL}$  at Week 12) and a positive anti-meningococcal response at Week 16 (defined as  $\text{IgG} \geq 3.0 \text{ mcg/mL}$  with at least a 3-fold increase compared to Week 12). These response criteria were developed based on the criteria for positive vaccine response in the assays used for determining anti-tetanus and anti-meningococcal IgG concentrations. The anti-tetanus response definition takes into account that some subjects may have high pre-vaccination anti-tetanus IgG levels and may therefore not be able to elicit the same increase in anti-tetanus IgG levels as those with low pre-vaccination levels.

The results should be generalisable to an adult population with AD. The age limit of 54 years is chosen to ensure that no subjects older than the meningococcal vaccine age limit of 55 years are included.

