SCORAD	Scoring Atopic Dermatitis
SCORAD50	At least 50% reduction in SCORAD score
SCORAD75	At least 75% reduction in SCORAD score
SOC	system organ class

Tdap	Tetanus, diphtheria and acellular pertussis
ULN	upper limit of normal
VAS	visual analogue scale

4 Introduction

The statistical analysis will be performed as outlined in the clinical trial protocol.

This statistical analysis plan is prepared before the unblinding of the trial and supplements the clinical trial protocol, which otherwise describes the originally planned statistical analyses of all endpoints in an intended exhaustive manner. The statistical analysis plan contains a more technical and detailed elaboration of some points related to the implementation of the statistical analysis already described in the clinical trial protocol.

In addition, the Statistical Analysis Plan includes supplementary statistical analyses and aspects that are introduced after the protocol.

Definition of vaccine response:

1. The definition and calculation of positive meningococcal response has been specified.

New analysis for the continuous other endpoints:

2. Analysis of a new tertiary estimand ('composite') for the continuous other endpoint 'Change from baseline to Week 16 in EASI score' is introduced. Analysis apply non-responder imputation for subjects who receive rescue medication.
3. A repeated measurements analysis of the percentage change from baseline in EASI score from baseline to Week 16 has been added.

The per protocol analysis set:

4. The definition of the per protocol analysis set as stated in the protocol has been updated with regards to handling of systemic rescue medication, baseline disease severity related to the EASI status and visit interval between administration of the vaccine and measurement of the vaccine response.

5 Trial analysis sets

The trial analysis sets are defined in the protocol and the following modifications to the analysis sets are introduced.

All subjects randomised to treatment who were exposed to IMP (tralokinumab/placebo) are included in the full analysis set and will be analysed for efficacy up to Week 16 (Visit 11). For subjects not exposed to IMP (tralokinumab/placebo), the decision to withdraw can't be biased by knowledge of the assigned treatment due to the blinding. This definition of the full analysis set implements the consideration mentioned in the protocol regarding special excluded cases with reference to ICH E9, Section 5.2.1.

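### SAP 6.6 drops the protocol's IgG ≥3.0 mcg/mL condition from the primary meningococcal endpoint while presenting its definition as the protocol's

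*SAP*

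**What the plan says.** The protocol synopsis lists the primary endpoint as "Positive anti-meningococcal response at Week 16 (IgG ≥3.0 mcg/mL with at least a 3-fold increase compared to Week 12". Panel 3, section 12 and section 14.3.5 (the primary analysis) give the same two conditions. Section 12 also explains their origin: "These response criteria were developed based on the criteria for positive vaccine response in the assays used".

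SAP 6.6 presents its definition as the protocol's own: "a positive anti-meningococcal response is defined as at least a 3-fold increase in specific IgG at Week 16", with Week 12 as the reference. It then says that four serogroups (A, C, W-135 and Y) are assayed separately, and sets a subject-level rule: "If data are available for 4 out of the four antigens, then the subject should be a responder against at least 3 of the antigens". When fewer antigens are available, the subject must respond to all of them. The 3.0 mcg/mL threshold appears nowhere in this section.

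The list of additions in SAP section 4 (Introduction) says only: "The definition and calculation of positive meningococcal response has been specified". It mentions no removed criterion and gives no rationale.

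**The concern.** SAP 6.6 attributes to the protocol a definition the protocol does not contain. It is also the only place that explains how four serogroup results become one responder status, so a programmer will work from it.

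The endpoint matters for three reasons:

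- It is one of two endpoints on which non-inferiority is judged, against a margin of -25%.
- Under the hierarchy in protocol 14.3.4, IGA 0/1 and EASI75 cannot be claimed unless it succeeds.
- The absolute threshold carries clinical meaning. Under the SAP text a rise from 0.2 to 0.6 mcg/mL counts as a positive response; under the protocol it does not.

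If the drug lowered the titre reached without often pushing the rise below 3-fold, the SAP rule would be less able to show it. The 80% planning rate in protocol 14.1 also appears in a document that knows only the two-part definition.

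**Working it through.** **1. The texts side by side**

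| Source | Week 16 IgG ≥3.0 mcg/mL | ≥3-fold rise from Week 12 |
|---|---|---|
| Protocol synopsis, Panel 3, sections 12 and 14.3.5 | required | required |
| SAP 6.6 | absent | required |

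The tetanus definition immediately before it in SAP 6.6 keeps both its cut-offs (1.0 and 2.5 IU/mL). The section therefore does not use a general shorthand that leaves thresholds to the protocol.

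**2. The plan's own power figures** (protocol 14.1)

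Inputs: 160 in the per protocol set, taken as 80 per arm from 1:1 allocation; 80% response in both arms; margin 25 points; one-sided 2.5%.

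- SE = √(2 × 0.8 × 0.2 / 80) = 0.0632.
- Power = Φ(0.25/0.0632 − 1.96) = 97.7% (stated: 98%).
- With 100 per arm, power is 94.8% for IGA 0/1 (30% v 10%) and 98.1% for EASI75 (40% v 15%).
- Product: 0.977 × 0.977 × 0.948 × 0.981 = 88.8% (stated: about 89%).

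Both figures reproduce. They neither support nor weaken the point about the definition.

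**3. Where the definitions part, per antigen**

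The protocol requires a fold rise of max(3, 3.0/Week 12 IgG). The SAP requires 3 throughout.

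| Week 12 IgG (mcg/mL) | Protocol requires | SAP requires |
|---|---|---|
| 0.1 | 30-fold | 3-fold |
| 0.2 | 15-fold | 3-fold |
| 0.5 | 6-fold | 3-fold |
| ≥1.0 | 3-fold | 3-fold |

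A result is reclassified only if Week 12 IgG is below 1.0, the rise is at least 3-fold and Week 16 IgG is below 3.0. The SAP rule can therefore only add responders.

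**4. Illustrative size for one antigen**

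Assumptions, none of them from the documents: Week 12 IgG and fold rise are log-normal and independent, each with log-SD 1, and the median rise is 12-fold. The SAP rate is then Φ(ln(12/3)) = 92%.

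| Median Week 12 IgG (mcg/mL) | SAP rule | Protocol rule | Gap (points) |
|---|---|---|---|
| 0.2 | 92% | 44% | 48 |
| 0.5 | 92% | 68% | 24 |
| 1 | 92% | 81% | 11 |
| 2 | 92% | 88% | 4 |

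Changing one assumption at a time, the gaps across the same medians become:

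- correlation of −0.5 between log Week 12 IgG and log rise: 51, 19, 6 and 1 points;
- median rise of 30-fold, independent: 30, 12, 5 and 1 points.

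**5. Illustrative effect on the non-inferiority test**

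Assumptions: 80 per arm, and 80% in each arm achieve a 3-fold rise. Some of these responders remain below 3.0 mcg/mL. Power is Φ((0.25 − difference)/SE − 1.96).

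| 3-fold responders below 3.0: placebo / tralokinumab | Protocol-rule rates: placebo / tralokinumab | SE | Power, protocol rule | Power, SAP rule |
|---|---|---|---|---|
| 10% / 10% | 72% / 72% | 0.0710 | 94.1% | 97.7% |
| 10% / 20% | 72% / 64% | 0.0735 | 63.8% | 97.7% |
| 10% / 30% | 72% / 56% | 0.0748 | 22.4% | 97.7% |

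These scenarios show that the choice of rule can decide the conclusion. They do not predict that it will.

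**The case against.** The omission itself is not in dispute. The case on the other side has four parts.

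- **The protocol may govern.** SAP section 4 says the analysis follows the protocol and that the SAP supplements it, so the omission may be a careless abbreviation. This stands to the extent that a different endpoint is analysed only if 6.6 is programmed as written. It does not remove the problem: a general sentence does not override the specific derivation rule, and two definitions of a primary endpoint still coexist.
- **The size is unknown.** This stands. The simulated rates rest on unverified assumptions, and the gap runs from about 1 to about 51 points over the variations tried. In the base model, 51%, 32%, 22% and 15% of those with Week 12 IgG below 1.0 are reclassified, for medians of 0.2, 0.5, 1 and 2. These are single-antigen rates, not the 3-of-4 endpoint, and they say nothing about the difference between arms.
- **The protocol does not mention serogroups.** This also stands. The protocol gives a single IgG threshold, and separate assays appear only in the SAP. Applying 3.0 mcg/mL to each serogroup is the natural reading alongside the 3-of-4 rule, but the sponsor should confirm it.
- **The 80% rate has no stated source.** This is correct; its link to the two-part definition is an inference.

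**Conclusion.** The concern holds. SAP 6.6 misstates a primary endpoint by omitting one of its two conditions, and the change is neither declared nor justified. Protocol 14.3.10 requires changes from the planned analysis to be described and justified. Elsewhere the SAP does this, for example for the EASI criterion and the immunosuppressant rule in the per protocol set. This must be corrected before unblinding.

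Two results need no distributional assumption, given a per-serogroup threshold: the requirements differ whenever Week 12 IgG is below 1.0 mcg/mL, and the SAP rule can only raise the response rate. The amount of the increase and its effect on the treatment difference depend on titre data that the documents do not contain.

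**What to change.** In SAP 6.6, define response for each serogroup as Week 16 IgG ≥3.0 mcg/mL and at least a 3-fold rise from Week 12, then apply the existing 3-of-4 rule and its fallbacks. Have the sponsor confirm that the threshold applies to each serogroup.

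If removing the threshold is intended, delete the attribution to the protocol and list the removal in SAP section 4 as a change to a primary endpoint, with a rationale. Pre-specify the protocol definition as a sensitivity analysis.

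The cost is one sentence and one derivation line, plus the sponsor's confirmation. No new data are needed. The observed response rate may be lower under the protocol definition.
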